Title of the study: The Pull Test To Determine Responders To Subacromial Injection In Patients With Shoulder Impingement

Trial registration: NCT02686671

Date: September 10, 2019

The study took place at Advanced Physical Therapy of Alaska facilities in Anchorage, Alaska.

Between March 2016 and October 2016, two investigators performed the following clinical tests to determine inter-examiner reliability using nine patients with lateral shoulder pain from a local physical therapy outpatient clinic: (1) shoulder flexion, external rotation, abduction and internal rotation passive ROM; (2) Spurling test; (3) Hawkins-Kennedy test; (4) Neer impingement test; (5) painful arc of abduction; and (6) Pull Test, which has been proposed as an shoulder impingement clinical test to differentiate SA bursitis from rotator cuff conditions. Following reliability testing, 29 participants were included from a consecutive convenience sample of 38 patients scheduled for fanwise SA CSI between the periods of January 2017 and February 2018. Past medical history was screened for inclusion and exclusion criteria.

For inclusion, the following criteria were: (1) age 18 to 80 years; (2) one or more positive shoulder clinical tests out of the following: Hawkins-Kennedy test, Neer impingement test, and painful arc of abduction; (3) lateral shoulder pain between 2/10 and 10/10 on Numeric Pain Rating Scale (NPRS) during resisted shoulder abduction; and (4) SPADI (total) score greater than or equal to 20.

For exclusion, the following criteria were: (1) large three-dimensional limitation with any passive range of motion (ROM) of the shoulder as compared to the contralateral side, to rule out adhesive capsulitis; (2) shoulder surgery within the last six months; (3) CSI to the involved shoulder within the past three months; (4) systemic inflammatory condition; (5) radiculopathy during cervical spine active ROM; (6) cervical spine pain as a primary complaint (7) lateral shoulder pain reproduction during Spurling test; (8) inability to undergo a follow-up phone call; (9) neurological disorders that would prevent clinical test performance and (10) pregnancy by self-report.

Study Design

A non-randomized, exploratory study, with repeated measures for pain and disability, was conducted to identify variables associated with successful fanwise subacromial (SA) corticosteroid injection (CSI) in participants with lateral shoulder pain.

Testing Sequence

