Each participant read slide presentation print-outs explaining study procedures followed by informed consent and medical history questionnaire. A pre-CSI pain questionnaire for average and current shoulder pain (Numeric Pain Rating Scale, NPRS) and Shoulder Pain and Disability Index (SPADI) were then completed to identify changes over the follow-up period.

Prior to their scheduled fanwise SA CSI as part of their plan of care, each participant within a private treatment room underwent a series of cervical and shoulder clinical tests similar to those performed during the reliability portion of testing by Investigator 1. For

the first two tests, participants exhibiting three-dimensional limitations of passive range of motion (ROM) within any plane indicative of adhesive capsulitis and/or a positive Spurling test were excluded from the study. If passive ROM and Spurling test were negative, the following shoulder clinical tests were performed with at least one required to be positive to participate further: (1) Hawkins-Kennedy test; (2) Neer impingement test; and (3) painful arc of abduction. Next, the Pull Test, involving comparison of shoulder pain produced between resisted shoulder abduction alone at 0° shoulder abduction and resisted shoulder abduction simultaneous with manually-performed humeral long-axis traction by the investigator was performed. Force level for resisted shoulder abduction alone was measured using a dynamometer (Chatillon® DF II Series Digital Force Gauge). For resisted shoulder abduction with traction, traction force was applied at mid-humerus level by one of the investigator's hands. The traction amount was determined by the maximum sulcus distance obtained between the lateral acromion and humerus monitored by the investigators' thumb of the other hand, with no inferior movement of the shoulder girdle detected. The participant was instructed to push outward from their distal humerus into the chest of the investigator positioned adjacent for this portion of the Pull Test. Maximum resisted shoulder abduction, with force level recorded, was the final test performed.

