Following clinical testing, each participant underwent fanwise SA CSI using a blind lateral approach performed by a pain medicine physician or physician assistant with over 30 years of experience. For the CSI, a standard solution consisting of 9cc of 0.25% bupivacaine with 1:200,000 epinephrine and 40 mg of triamcinolone (Kenalog®) was administered using a 9 cm 22- or 25-gauge needle. Manually-performed humeral long-axis traction was performed by a medical assistant when a patient was unable to relax, which can affect the entry point into the AHI.

Approximately 30-minutes post-CSI (to allow for anaesthetic to take effect and post-injection vital signs to be charted by a medical assistant), Investigator 2 performed the previous series of shoulder clinical tests in the same order except for shoulder passive ROM and Spurling test, which were not performed. The Pull Test was not performed, however, resisted shoulder abduction alone was included as a test to compare with the pre-CSI result. The second investigator was blind to the results of pre-CSI testing with exception of force applied during resisted shoulder abduction pre- CSI, with a similar force used for resisted shoulder abduction post-CSI to identify pain level change. Maximum resisted shoulder abduction was performed last with force and pain level recorded. One-week and six-week phone follow-ups were conducted post- CSI. Each participant was allowed to continue their current physical therapy regimen if applicable.

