Title of the study: The Pull Test To Determine Responders To Subacromial Injection In Patients With Shoulder Impingement

Trial registration: NCT02686671

Date: September 10, 2019

The study took place at Advanced Physical Therapy of Alaska facilities in Anchorage, Alaska.

Statistical Analysis

Data were analyzed using SPSS software (version 20.0). Descriptive statistics were used to record demographic characteristics, Numeric Pain Rating Scale (NPRS) and Shoulder Pain and Disability Index (SPADI) scores.

Inter-examiner **reliability** was assessed using kappa and percent agreement. **Friedman test, with Wilcoxon signed-ranks test** for pairwise comparisons, was used to determine if SPADI (total) score and average NPRS demonstrated significant changes over time. Effect size (r) was calculated to determine the magnitude of the difference for each pairwise comparison. Mean differences (Mann-Whitney) in average NPRS and SPADI (total) score for positive and negative Pull Test groups were analyzed for follow-up periods. Effect size estimates of variance (r^2) were calculated to identify the percentages of variability in the dependent variables (SPADI, NPRS) explained by each Pull Test group.

Fisher's exact test was calculated to evaluate dichotomous variable association, including clinical test outcomes, gender, and hand dominance, with SPADI (total) score one-week and six-week post-CSI. **Univariate regression** was used to determine if demographics, clinical variables and clinical tests were predictive of successful response one-week and six-week post-CSI ($p \leq .200$). Sensitivity, specificity, positive and negative predictive values, positive and negative likelihood ratios, and odds ratios were calculated for shoulder clinical tests.

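### The only effect size labelled for the Pull Test group comparison is r², worded as a share for each group; the plan adds no baseline adjustment and no interval to the difference in points

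*SAP*

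**What the plan says.** The SAP's Statistical Analysis section sets out the Pull Test comparison in two sentences. The first gives the test: "Mean differences (Mann-Whitney) in average NPRS and SPADI (total) score for positive and negative Pull Test groups were analyzed for follow-up periods". The second adds r² as an effect size, "to identify the percentages of variability in the dependent variables (SPADI, NPRS) explained by each Pull Test group". The section gives no formula for r² and mentions no confidence interval for any estimate. It describes no baseline adjustment, and its regression is univariate.

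A separate effect size, r, follows the Friedman and Wilcoxon tests of change over time: "Effect size (r) was calculated to determine the magnitude of the difference for each pairwise comparison". That one is tied to a comparison, not to a group.

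The Protocol supplies the rest:
- On sample size, "29 participants were included from a consecutive convenience sample of 38 patients".
- Its Study Design section calls the study non-randomised and exploratory.
- Its Testing Sequence section has average and current NPRS and the SPADI completed before the injection.
- On timing, "One-week and six-week phone follow-ups were conducted" after the injection.

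**The concern.** Variance is explained by the contrast between the two groups. Neither group explains a part of its own, so a reader who takes the sentence literally will look for two percentages per outcome and time and cannot know what either would measure.

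The larger matter is what the plan offers for the comparison that gives the study its title. The only quantity it calls an effect size there is a percentage without units or sign. It does name mean differences, but attaches them to a rank test, which does not estimate a mean difference, and gives them no interval.

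Pull Test status is also a patient characteristic and not an allocation. Positive and negative patients may start from different SPADI or NPRS levels, and a follow-up difference that ignores this mixes the starting level with the response.

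**Working it through.** The documents report no r², no SD, no number of Pull Test positives and no sample size calculation, so there is no figure of the plan's own to reproduce. From the documents come N = 29, two outcomes ("SPADI (total) score and average NPRS") and two follow-up times. Everything else below is assumed and marked so.

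**1. How many r² values exist.** Let g = 1 for positive and 0 for negative. The opposite coding is 1 − g, and corr(1 − g, y) = −corr(g, y), so the squares are equal. A numerical check with simulated scores (N = 29; 8, 10, 14 or 20 positives) agreed every time. With 14 positives, both codings gave .2027 on raw scores and .2058 on ranks. The count is therefore 2 outcomes × 2 times = 4 values, not 8.

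**2. Does the missing formula matter?** Only slightly. In that same data set the squared rank correlation equals Z²/(N − 1) = .2058, and Z²/N = .1987. Their ratio is 28/29. The formula should be stated, but the choice moves little.

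**3. What r² leaves open.** On raw scores with a pooled SD and 27 degrees of freedom, the standardised difference is

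d = √[ r²/(1 − r²) × 27 × (1/n₁ + 1/n₂) ].

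For an assumed r² = .20, √(.25 × 27) = 2.598. The 95% CI is d ± 2.052 × √(1/n₁ + 1/n₂).

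| Assumed split | √(1/n₁ + 1/n₂) | d (SD units) | 95% CI |
|---|---|---|---|
| 15/14 | 0.372 | 0.97 | 0.20 to 1.73 |
| 20/9 | 0.401 | 1.04 | 0.22 to 1.87 |
| 24/5 | 0.492 | 1.28 | 0.27 to 2.29 |

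In points the answer also depends on the SD. The same r² of .20 means 14.5 SPADI points (95% CI 3.0 to 25.9) at an assumed SD of 15 and a 14/15 split, and 27.0 points (5.7 to 48.3) at an assumed SD of 25 and an 8/21 split.

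**4. What baseline adjustment costs or gains.** Mean 95% CI half-widths for the group difference, in SD units, from simulation with groups alike at baseline apart from chance:

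| Assumed baseline–follow-up correlation | 15/14: unadjusted → adjusted | 24/5: unadjusted → adjusted |
|---|---|---|
| 0 | .756 → .773 | 1.000 → 1.020 |
| .5 | .757 → .671 | 1.001 → .885 |
| .7 | .755 → .550 | .999 → .728 |

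At 15/14 the ratios are 1.02, .89 and .73: about 2% wider, 11% narrower and 27% narrower. They follow 1.0225 × √(1 − ρ²), where 1.0225 = .773/.756. That product reaches 1 at ρ = √(1 − 1/1.0225²) ≈ .21, so a correlation above about .2 is needed before the interval narrows.

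**5. If the groups do differ at baseline.** For an assumed true gap of 1 SD at 15/14, the squared correlation between group and baseline is about pq/(1 + pq), with pq = (15 × 14)/29² = .250, which gives .200. The adjusted interval widens by 1/√(1 − .200) = 1.118. The ratios become about 1.0225 × 1.118 = 1.14, .886 × 1.118 = .99 and .728 × 1.118 = .81. In that case adjustment serves mainly to remove the imbalance, and the gain in width is small unless the correlation is high.

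**The case against.** The strongest reply is that the defect is one word. The preceding sentence compares the positive and negative groups, so the natural reading is variability explained by the grouping; the label is then wrong and the number is right. That stands.

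Three further objections also stand in part:
- The SAP already names mean differences, so a difference in points, with its direction, is nominally planned. What is missing is the interval, the adjustment and an estimator that goes with the method. The absence of intervals runs through the whole SAP and is not special to r².
- The SAP does not say whether the Mann-Whitney test used follow-up scores or changes from baseline. If it used changes, baseline is partly handled already, though the plan does not say so.
- The documents are dated September 2019 and written in the past tense, after inclusion ran from January 2017 to February 2018. Rewording changes no enrolment, error rate or decision.

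A reader might infer that separate variance shares were computed for each group, or that r² was taken within each group over time. The documents support neither: the first does not exist as a quantity, and the Friedman and Wilcoxon tests are not described as run by Pull Test group. A reader might also take the wide uncertainty of r² at N = 29 as proof of the wording fault, or expect a favourable percentage to fade once an interval is shown. The uncertainty would be the same under correct wording, and no percentage is reported.

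**Conclusion.** The point holds as a minor matter of reporting and estimation. The wording about each group is incorrect, because there are four r² values and none belongs to a single group; but it is probably loose phrasing, and nothing shows that a wrong analysis was run. P-values, sensitivity, specificity, predictive values, likelihood ratios and odds ratios are untouched.

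What merits a change is that the study's central comparison, between groups that were not randomised, rests on a unitless percentage and on mean differences with neither interval nor stated baseline adjustment. An r² of .20 would be compatible with differences from 0.97 to 1.28 SD over the splits considered. Most of that spread comes from the uneven 24/5 split; between 15/14 and 20/9 it is only 0.97 to 1.04.

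The r² value, splits, SDs, normal distributions and correlations are all assumptions. N = 29 is the number included; the number reached at each call is not stated, and any loss would widen the intervals. The preference for a difference in points is a judgement, resting on the fact that r² lacks units and sign.

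**What to change.** Keep the Mann-Whitney test. For SPADI (total) and average NPRS, at one week and at six weeks, add one positive-versus-negative difference in points, adjusted for the baseline value of the same score, with its 95% CI and the number of patients in each group at that time. State whether the Mann-Whitney test uses follow-up scores or changes.

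If r² is kept, describe it as the share of variability explained by Pull Test result (positive versus negative), one value per outcome and time. Give its formula, and if it is computed from Z, say that it refers to ranks.

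The cost is one reworded sentence, a few lines of code on data already collected, and one degree of freedom in each of four models. With groups alike at baseline, the interval is about 2% wider if baseline carries no information and narrower once the correlation passes about .2. With a large baseline gap it may be wider (about 14% in the assumed 1-SD case with no correlation). The adjusted difference also answers a slightly different question, comparing patients with the same starting score, and the report should say so.

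### Univariate p ≤ .200 is the only stated rule for calling a variable predictive; if nothing is truly associated, about 1.2 false predictors per visit are expected from six candidates

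*SAP*

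**What the plan says.** The SAP (Statistical Analysis, last paragraph) states that univariate regression "was used to determine if demographics, clinical variables and clinical tests were predictive of successful response one-week and six-week post-CSI", and closes that sentence with p ≤ .200 in parentheses. No other criterion is attached to the word *predictive*.

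The sentence before it plans Fisher's exact test for "dichotomous variable association, including clinical test outcomes, gender, and hand dominance" against SPADI at the same two visits. The sentence after it, the last in the SAP, plans accuracy measures and says that "odds ratios were calculated for shoulder clinical tests". No multivariable model, validation step or multiplicity adjustment appears in either document.

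The protocol (Study Design) calls the study exploratory and says it "was conducted to identify variables associated with successful fanwise subacromial (SA) corticosteroid injection (CSI"). On sample size, the protocol reports that "29 participants were included from a consecutive convenience sample of 38 patients".

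**The concern.** A cut-off of .200 can be reasonable as a first screen, where a false entry costs little because a later model or a new sample will test it. Here no later step is described, so passing the screen is the finding. The rule accepts about one unrelated variable in five and applies to an unlisted number of variables at two visits. A reader therefore cannot tell how many were tried.

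This matters because identifying variables associated with a successful injection is the study's stated aim. The Pull Test is less exposed, since it also has Mann-Whitney, Fisher and accuracy analyses. Demographic and clinical candidates that are not dichotomous have no other planned analysis against success, so for them the .200 rule is the whole case.

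**Working it through.** The documents give no expected error count, so there is no figure of the plan's own to reproduce.

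**Inputs from the documents**
- Per-test threshold: .200 (SAP, Statistical Analysis).
- Visits: 2, at one week and six weeks.
- Sample size: 29 (protocol, opening section).
- Candidates: the regression sentence gives only three open classes. Six dichotomous variables can be identified elsewhere: gender and hand dominance (SAP, Fisher sentence), and Hawkins-Kennedy, Neer, painful arc and Pull Test (protocol, Testing Sequence). Six is an assembled count, not the plan's list.

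**Expected false predictors if no candidate is associated** (number of tests × 0.20; correlation does not affect it)
- One visit: 6 × 0.20 = 1.2.
- Both visits: 12 × 0.20 = 2.4.
- An assumed 10 to 15 candidates over both visits: 20 × 0.20 = 4.0 to 30 × 0.20 = 6.0.

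**Chance of at least one, at the nominal 20% rate**
- Independent tests: 1 − 0.8^6 = 0.738 for one visit; 1 − 0.8^12 = 0.931 for both.
- Correlated tests, simulated with normal z-scores and an assumed correlation of 0.7 between visits: 0.80 over both visits if candidates correlate 0.5, and 0.70 if they correlate 0.7. Per visit these are 0.62 and 0.52.

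**Actual per-test rate at n = 29.** The SAP does not name the type of regression. Logistic regression of success on a binary candidate is assumed, with a null success rate of 0.4 to 0.7. Exact enumeration of the 2×2 tables, counting zero-cell tables as not significant for Wald, gives:

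| Split of candidate | Wald | Likelihood ratio |
|---|---|---|
| 15/14 | 0.205–0.214 | 0.235–0.265 |
| 23/6 | 0.127–0.177 | 0.208–0.240 |
| 26/3 | 0.011–0.087 | 0.260–0.356 |

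Uneven splits are plausible for the three impingement tests, because "the following shoulder clinical tests were performed with at least one required to be positive to participate further".

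**Allowing for uneven splits.** The three entry tests take the Wald rates above, the other three stay at 0.20, and both visits count.
- At 23/6, expected count: 2 × (3 × 0.127 + 0.6) = 1.96 to 2 × (3 × 0.177 + 0.6) = 2.26. Chance of at least one if independent: 1 − 0.873^6 × 0.8^6 = 0.884 to 1 − 0.823^6 × 0.8^6 = 0.919.
- At 26/3, expected count: 2 × (3 × 0.011 + 0.6) = 1.27 to 2 × (3 × 0.087 + 0.6) = 1.72. Chance if independent: 0.755 to 0.848.
- Adding the correlations above (0.5 or 0.7 between candidates, 0.7 between visits): 63% to 78% at 23/6 and 55% to 69% at 26/3 over both visits. Per visit: 45% to 60% and 38% to 50%.

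**What a passing result can look like.** Assume 9 of 15 succeed with the finding and 5 of 14 without it.
- OR = (9 × 9)/(6 × 5) = 2.70.
- SE of log OR = √(1/9 + 1/6 + 1/5 + 1/9) = 0.767.
- 95% CI = exp(0.993 ± 1.96 × 0.767) = 0.60 to 12.15; Wald p = .196.

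This result would be called predictive.

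**The case against.** The strongest reply is that the reading rests on silence. The .200 stands as a bare parenthesis in a short SAP, and a screening step may have been intended whose sequel was left out. The study is openly exploratory, and at n = 29 a strict threshold would miss real candidates, which is also an error. Much of the analysis does not depend on .200, including that of the test in the study's title. The data were already collected when the documents were dated, and six candidates are not what the regression sentence lists.

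Some of this stands. The count of six is assembled, though the regression also covers unlisted demographics and clinical variables, so six is more likely too few than too many. The independence probabilities are upper figures. With correlation and Wald tests on very uneven splits, the chance at a single visit falls to even odds or below, while likelihood-ratio testing raises the per-test rate. The Pull Test is partly protected.

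The rest does not rescue the rule. If a next step was meant, it is not in the plan, and the text attaches .200 directly to *predictive*. The exploratory label excuses the absence of formal error control, but not a claim of prediction at a one-in-five error rate. The loss of power argues for reporting estimates with intervals rather than for a looser verdict.

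**Conclusion.** The concern holds and should be fixed before results are reported under this rule. For six candidates with none truly associated, the nominal expectation is 1.2 false predictors per visit and 2.4 over both. If the three entry tests are very unevenly split and Wald tests are used, the two-visit expectation falls to between 1.3 and 2.3. At least one false predictor over both visits is more likely than not in every scenario examined, from 55% to 93%.

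These figures rest on the assembled count of six, an assumed logistic form, assumed splits, success rates and correlations, and no true association. What does not depend on them is that the only stated rule for *predictive* is univariate p ≤ .200, with no list of candidates and nothing after it.

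**What to change.** Revise the SAP's Statistical Analysis section as follows:
- Remove p ≤ .200 as the criterion for *predictive*, and make no claim of prediction from it.
- List every candidate examined in the regression and state how many there were.
- Report the odds ratio with 95% CI for each candidate at both one and six weeks, whatever its p-value.
- Label these results hypothesis-generating, with type I error uncontrolled and validation in a new sample needed.
- If a main predictor or time point is singled out now, disclose that choice as post hoc.

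The cost is SAP wording and re-tabulation, with no new data. Odds ratios are already planned for the shoulder clinical tests, so the additions are their intervals, the remaining candidates and the count. The downside is that fewer variables, possibly none, can be called predictive.
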